13.4.3. Event of Special Interest

Not applicable - No events of special interest are expected for this study.

13.5. Reporting of Pregnancy

Subjects reporting pregnancy (by self-report) during the study screening section of this study will be discontinued as a screen failure. Subjects reporting pregnancy (by self-report) during the study will be discontinued after the event is recorded as an Adverse Event. Once discontinued, pregnant Subjects and their fetuses will not be monitored for study related purposes. Pregnant Subjects are not discontinued from contact lens or solution related studies for safety concerns, but due to general concerns relating to pregnancy and contact lens use. Specifically, pregnant women are discontinued due to fluctuations in refractive error and/or visual acuity that occur secondary to systemic hormonal changes, and not due to unforeseen health risks to the mother or fetus.

14. STATISTICAL METHODS

14.1. General Considerations

Statistical Analysis will be undertaken by the sponsor. A general description of the statistical methods to be implemented in this clinical trial is outlined below.

All data summaries and statistical analyses will be performed using the SAS software Version 9.4 or higher (SAS Institute, Cary, NC). Throughout the analysis of data, the results for each subject/eye will be used when available for summarization and statistical analysis. Unscheduled visits will be summarized separately and will be excluded from the statistical analysis.

Summary tables (descriptive statistics and/or frequency tables) will be provided for all baseline variables, efficacy variables and safety variables as appropriate. Continuous variables will be summarized with descriptive statistics (n, mean, standard deviation [SD], median, minimum and maximum). Frequency count and percentage of subjects or eyes within each category will be provided for categorical data.

14.2. Sample Size Justification

This is an exploratory study to generate initial data for assessing a computational vision model. As such, the sample size was not determined based on any power analysis with regard to the primary endpoint. The collected data will be used to design future studies, if necessary.

The planned sample size (75 to enroll and 50 to complete) was selected to enroll different categories of myopic presbyopes including previous MF CL wearers, Single vision CL wearers and Subjects who are neophyte to CL wear. Efforts will be made to enroll subjects in all three categories without specific targets to be achieved.

All analysis will be conducted on the per-protocol population defined in section 14.3.

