
Study Design
	
This is a prospective, single-arm, and bilateral dispensing study.
 
There will a total of 6 visits:
 
Visit 1 (Screening and Baseline-day 0): consent, eligibility confirmation, pre-fit interview, and evaluation assessments
 
Visit 2 (Baseline & dispensing-Day 0): personality test, evaluation assessments, study lens fitting, CL insertion and removal training (non-CL wearers, up to 1 additional training appointments are permitted), subjective responses to CL performance, dispensing of CL
 
Visit 3 (1-week follow-up, lens power optimization-Day 7±3 from Visit 2): CL power optimization, lens fit assessment, evaluation assessments
 
Visit 4 (2-week follow-up- Day 7±3 from Visit 3): lens fit assessment, evaluation assessments, subjective responses to CL performance
 
Visit 5 (6-week follow-up Day 28±6 from Visit 2-): lens fit assessment, evaluation assessments, subjective responses to CL performance
 
Visit 6 (12-week follow-up Day 42±6 from Visit 2-): Post-fit interview, lens fit assessment, evaluation assessments, subjective responses to CL performance

	
Study exit: Investigator recommendation, if applicable (study CLs suitable/not suitable to prescribe, plus investigator reasons where not suitable is indicated), exit procedures. See the flow chart at the end of the synopsis table for the schematic of the study visits and procedures of main observations (Figure 1).

Sample Size	
The target is to dispense lenses to 50 presbyopic Subjects who had no experience with soft multifocal contact lens wear for >2 years; total sample size 50. Enrollment is potentially likely to be up to approximately 75 to account for screen failures.

Study Duration	
The study is anticipated to have a duration of approximately 9 months in total, with enrollment lasting approximately 6 months.

Anticipated Study Population	
All eligible Subjects will have no experience with soft multifocal contact lenses (MF CLs) for >2 years. The study population includes previous MF CL wearers, single vision CL wearers and subjects who are neophyte to CL wear; The target is to include myopes only, with a maximum reading addition of +1.75 DS.
 
There are no sex or race requirements. All subjects need to be in the presbyopic age group ie, ≥ 40 years old and with a minimum add of +0.75 D.
 
Current MF CL wearers and current monovision wearers are not eligible.

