4.3. Enrollment Target and Study Duration

- Up to approximately 75 Subjects will be screened, with a target of dispensing product to up to 50 subjects who may complete the study. Subjects will be recruited using CORE records and advertising approved by the University of Waterloo (UW) Office of Research Ethics (ORE).
- Point of enrollment in this study will be execution of informed consent.
- There will be a total of 6 study visits including the study screening visit during which consent, eligibility confirmation, interview and evaluation assessments will be conducted.
- The study will last approximately 9 months and include a 6 month enrollment period.
- This will be a single site study. Study visits will be conducted at Centre for Ocular Research & Education (CORE), University of Waterloo, Ontario.

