5.2. Masking

Not applicable. There will be no masking in this study.

Subjects who are discontinued will not be replaced.

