8.2. Withdrawal/Discontinuation from the Study

A participant will be withdrawn from the study for any of the following reasons:

- Participant death during the study period
- Participant withdrawal of consent

- Participant not compliant to protocol (*not compliant with or not able to follow study procedures, or study procedures/interviews /assessments could not be conducted*)
- Participant lost to follow-up
- Participant no longer meets eligibility criteria (e.g. the participant becomes pregnant)
- Participant develops significant or serious adverse event during the study visit (e.g. a heart attack)
- Subjects presenting with a Corneal Infiltrative Event (CIE), or an eye infection
- Subject develops significant or serious adverse events causing discontinuation of study lens wear (missing more than half of the required days of lens wear in-between visits will lead to discontinuation, e.g. wearing the lens for only 1 day instead of the minimum of 4 days between visits 2 and 3)
- Investigator's clinical judgment regarding the participant safety reasons (that it is in the best interest of the participant to stop the study visit)
- Participant missed *two consecutive* study visits
- Participant not compliant with study lens wear schedule
- Participant not successfully dispensed due to lack of efficacy and safety including poor vision, poor comfort or unacceptable fit

For discontinued Subjects, the Investigator will:

- not complete the scheduled visit procedures
- Complete the Final Evaluation, indicating the reason that the participant was discontinued from the study
- Record the spherocylindrical refraction with best corrected distance visual acuity if applicable (i.e. if this was already measured during the same day) otherwise perform a spherocylindrical refraction and record the exit distance visual acuity.
- Collect used test article(s) (worn or brought to the visit) from the participant and discard them, unless otherwise stated in Section 7.2
- Collect all unused test article(s) from the participant

An additional participant may be enrolled if a participant discontinues from the study prematurely.

In cases where a participant is lost to follow-up, every possible effort must be made to contact the participant and determine the reason for discontinuation/withdrawal. The measures taken to follow up must be documented including two written attempts and a certified letter (or equivalent) as the final attempt.

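### Section 14.2 plans for 50 completers, but 50 is also the number dispensed; no dropout is allowed for, and sections 5.2 and 8.2 disagree on replacement

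*Combined protocol and SAP*

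**What the plan says.** The sample size appears in three places.

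- Section 14.2: "The planned sample size (75 to enroll and 50 to complete". It adds that the size does not come from a power analysis and that all analysis uses the per-protocol population.
- Synopsis, Sample Size: "The target is to dispense lenses to 50 presbyopic Subjects", and then "Enrollment is potentially likely to be up to approximately 75 to account for screen failures".
- Section 4.3: "Up to approximately 75 Subjects will be screened, with a target of dispensing product to up to 50 subjects who may complete the study". It also fixes when a subject counts as enrolled: "Point of enrollment in this study will be execution of informed consent".

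Two sections deal with replacement.

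- Section 5.2: "Subjects who are discontinued will not be replaced".
- Section 8.2: "An additional participant may be enrolled if a participant discontinues from the study prematurely".

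Three further sections bear on the point. Section 8.1 counts a subject as complete only after all six visits. Section 14.3 limits the per-protocol set to subjects who completed all visits without substantial deviation. Section 14.9 names dropout as a main expected source of missing data and triggers a multiple-imputation sensitivity analysis if dropout exceeds 15%. It gives no expected rate.

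**The concern.** The figure of 50 has two meanings. In section 14.2 it is the number who finish; in the synopsis and section 4.3 it is the number who receive lenses. These agree only if nobody who is dispensed lenses drops out. The margin between 75 and 50 does not cover such loss, because enrollment is counted from consent and the synopsis assigns the margin to screen failures.

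Zero dropout also fits poorly with the rest of the protocol. Section 7.2 requires discontinuation after dispensing for unacceptable vision, unacceptable fit or failure of the acuity criterion. Completion is itself part of the definition of a successful wearer, so discontinuation is one of the designed routes into the unsuccessful group.

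What is at stake is the number analysed. Because every analysis is per-protocol, each dropout reduces it, and substantial deviations reduce it further. A reader who takes 50 from section 14.2 as the analysis size will overstate it. The same holds for the Quest class in the primary hypothesis, which is only part of that set.

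**Working it through.** **Inputs from the documents.** About 75 enrolled (14.2, synopsis); 50 dispensed (synopsis; 4.3 says up to 50); 50 to complete (14.2).

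**Assumption.** Let d be the share of dispensed subjects who do not complete. The documents give no value, so a range is shown.

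**Step 1: reproduce the stated figure.** Expected completers = 50 × (1 − d). This equals 50 only at d = 0. The gap of 75 − 50 = 25 is one third of those enrolled (25/75 = 33.3%), and the synopsis uses it for screen failures.

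**Step 2: section 5.2 applies (no replacement).** The chance that all 50 complete is (1 − d)^50, treating subjects as independent. The number to dispense for 50 expected completers is 50/(1 − d), rounded up.

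| Assumed d | Expected completers of 50 | Chance all 50 complete | Dispensed needed for 50 completers |
|---|---|---|---|
| 5% | 47.5 | 7.7% | 53 |
| 10% | 45 | 0.5% | 56 |
| 15% | 42.5 | 0.03% | 59 |
| 20% | 40 | 0.001% | 63 |

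**Step 3: section 8.2 applies (additional participants allowed).** Fifty completers can then be reached, but dispensing exceeds the 50 in section 4.3. To stay within 75 enrolled, the share lost before dispensing must not exceed 1 − 53/75 = 29% at d = 5%, 1 − 56/75 = 25% at 10%, 1 − 59/75 = 21% at 15%, or 1 − 63/75 = 16% at 20%. All are below the one third implied by 75 and 50. If one third were lost, enrollment would have to be 1.5 times the number dispensed, rounded up: 80, 84, 89 or 95.

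**Step 4: effect on precision.** Taking an assumed success proportion of 85% over the whole analysed sample, the 95% half-width is 1.96 × √(0.85 × 0.15/n). This is 9.9 percentage points at n = 50 and 10.8 at n = 42 (42.5 rounded down), a difference of 0.9 points. The primary criterion concerns only the discontented and driven class, whose size is not stated. At the same success proportion its interval would be wider than either figure.

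**The case against.** The strongest reply is section 8.2. If additional participants may be enrolled, 50 completers are attainable, and Step 3 shows that this can fit within 75 if fewer subjects fail before dispensing. The 50 in the synopsis and section 4.3 is also worded as a target, the 75 is approximate, and section 4.3 says only that those dispensed may complete. The study is exploratory, its size is not derived from power, and the precision lost is small. No calculation in the plan is wrong; the fault lies in inconsistent statements.

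Most of this stands, and it rules out three stronger readings.

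- A reader might infer that 50 completers cannot be delivered. The documents do not support that: they are possible at zero dropout, or if section 8.2 governs.
- A reader might take 15% as the plan's expected dropout. Section 14.9 uses it only as the trigger for a sensitivity analysis.
- A reader might infer that stated power is lost. Section 14.2 claims none.

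The reply does not remove the inconsistency. Section 8.2 conflicts directly with section 5.2, and using it would take dispensing above the figure in section 4.3. Under either rule, the three statements of sample size do not describe the same plan.

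**Conclusion.** The point holds as a misstated planned number together with a contradiction on replacement. Section 14.2 calls 50 the completers, while the synopsis and section 4.3 make it the number dispensed, with no allowance for the dropout that section 14.9 expects. If section 5.2 governs, the expected shortfall from 50 is 2.5 to 10 completers at assumed dropout of 5% to 20%, and the expected per-protocol set can be no larger than the number completing. If section 8.2 governs, 50 can be reached, but the dispensing figure is then too low.

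The shortfall rests on the assumed dropout range. The chance that all 50 finish also rests on independence between subjects, and the half-widths rest on an assumed 85% success proportion. The effect on precision is modest. The reason to correct it is that every planned analysis rests on this number.

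**What to change.** - Restate section 14.2 as about 75 to enroll and up to 50 to be dispensed. Add the expected number of completers, as the upper limit of the expected per-protocol size, under a stated dropout assumption: for example 40 to 45 at 10–20%.
- Use the same terms in the synopsis and section 4.3, so that 50 has one meaning.
- Reconcile sections 5.2 and 8.2 on replacement. If additional participants are allowed, adjust the dispensing and enrollment figures to match.
- Do not describe the 50 dispensed as the analysis size while all analysis remains per-protocol. That would contradict sections 14.2 and 14.3 and amount to a change of analysis population.

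If 50 dispensed is kept, this is a change of wording with no extra subjects and no effect on any power statement. The cost is a slightly less favourable stated number.

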1. INTRODUCTION AND BACKGROUND

Despite the growing number of presbyopes by aging, only a small fraction of presbyopic patients can be categorized as successful habitual soft multifocal (MF) contact lens (CL) wearers. Some habitual spectacle/single vision contact lens wearers in the presbyopic age group may have tried soft MF CLs in the past and dropped out from MF CL wear for various reasons. This single-arm study was designed to investigate the possible underlying reasons for achieving success or dropping out from soft MF CL wear.

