***Likely to be Successful Group definition:**

- Completed all required study visits, AND ...
- Investigator would recommend the study CLs, AND ...
- The subjects' response on the MRD "overall quality of vision" and "overall comfort" questions as good, very good or excellent.

Likely to be Unsuccessful Group definition:

- Not meeting the definition of successful.

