14.3. Analysis Populations

Safety Population:

All Subjects who were administered any test article excluding Subjects who drop out prior to administering any test article. At least one observation should be recorded.

Per-Protocol Population:

All Subjects who have successfully completed all visits and did not substantially deviate from the protocol as determined by the trial cohort review committee prior to database hard lock (Per-Protocol Population). Justification of excluding Subjects with protocol deviations in the per-protocol population set will be documented in a memo to file.

Intent-to-Treat (ITT) Population:

All Subjects regardless of actual treatment and subsequent withdrawal from study or deviation from protocol. At least one observation should be recorded.

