14.5. Primary Analysis

Likelihood to be a successful lens wearer vs. Quest questionnaire classification

The successful lens wear will be converted to a binary response the same as in the previous analysis. The proportion of response (“1”) will be analyzed using a generalized linear mixed model with a binary distribution and logit link function for all questions. Each model will include the experimental design factors: Quest questionnaire classification as the fixed effect; and subject as the random effect. Other baseline characteristics known to be important such as age, sex, and/or add power will be included as fixed covariates when appropriate.

The proportion of successful lens wear for the subjects classified as being “discontented and driven” will be calculated with 95% CI for least square mean. If the lower limit of the CI is greater than 75%, the statistical superiority will be concluded.

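### The analysis set is limited to completers, although non-completion is itself a failure of the primary endpoint, so those failures never enter the proportion tested against 75%

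*Combined protocol and SAP*

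**What the plan says.** Section 2.2 sets three conditions for the successful group. The first is "Completed all required study visits"; the others are the investigator's recommendation and favourable ratings on two MRD items, overall vision and overall comfort. The unsuccessful group is everyone else: "Not meeting the definition of successful".

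Section 14.2 then says: "All analysis will be conducted on the per-protocol population defined in section 14.3". Section 14.3 defines that population as "All Subjects who have successfully completed all visits and did not substantially deviate from the protocol". The same section defines an intent-to-treat set, "All Subjects regardless of actual treatment and subsequent withdrawal from study or deviation from protocol", but no analysis is assigned to it.

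Section 14.5 estimates the success proportion in the discontented-and-driven Quest class with a 95% confidence interval and gives this rule: "If the lower limit of the CI is greater than 75%, the statistical superiority will be concluded". Section 14.9 does not impute missing values in the main analysis. It adds a multiple-imputation sensitivity analysis only when dropout exceeds 15%.

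The introduction gives the purpose: "This single-arm study was designed to investigate the possible underlying reasons for achieving success or dropping out from soft MF CL wear".

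**The concern.** A subject who does not complete is unsuccessful under section 2.2 and is also removed under sections 14.2 and 14.3. The plan defines a kind of failure that its analysis can never count. Within the analysed set the completion condition is constant, so only the investigator's recommendation and the two MRD ratings can separate the groups.

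The removed subjects include lens failures. After dispensing, section 7.2 discontinues subjects for unacceptable vision (steps 3.8, 4.5, 5.5), a required power that is not available (3.8), unacceptable fit (3.9, 4.7, 5.7) or an unacceptable exit visual result (3.21, 4.17, 5.12). Completers with poor ratings or no recommendation do stay in as failures.

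Two things are at stake. The superiority statement rests on a proportion from which some failures have been taken out. The Quest and ocular-predictor analyses also lose the dropouts whose reasons the study was set up to examine, although step F.4 records why they stopped and step F.5 collects their questionnaires.

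**Working it through.** **Inputs from the plan.** Threshold 75%, judged by the lower limit of a 95% interval (14.5); overall type I error 5% (14.4), so nominally 2.5% on the lower side; 75 to enrol and 50 to complete (14.2); 15% dropout as the trigger for imputation (14.9). Section 14.2 says the sample size comes from no power calculation, so there is no figure to reproduce; 50/75 = 66.7% is only the implied ratio.

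**Not in the plan, so assumed.** The number of subjects in the discontented-and-driven class, and the dropout rate. All figures below concern the completion requirement alone, before any exclusion for deviations.

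**1. Direction.** With s successes among N dispensed and d non-completers, all of them failures under 2.2, the crude proportion goes from s/N to s/(N − d). This cannot be lower, and it is higher whenever s and d are both positive.

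**2. Point estimate.** With a true 75% among dispensed subjects and dropout d, the completer proportion is 0.75/(1 − d):
- 5%: 0.75/0.95 = 78.9%
- 10%: 0.75/0.90 = 83.3%
- 15%: 0.75/0.85 = 88.2%

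**3. Effect on the decision.** The exact lower limit is the 2.5th percentile of Beta(x, n − x + 1). The logit-Wald limit is logit(p) − 1.96/√(np(1 − p)), transformed back; without covariates it stands in for the 14.5 model.

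Assume 30 of 50 dispensed subjects are in the class: 25 successes, 1 completer who fails, 4 non-completers. Dropout is 4/30 = 13.3%, so 14.9 triggers nothing if overall dropout is similar. The extreme case puts all 50 in the class, with 40 successes and 5 non-completers.

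| Case | Proportion | Exact limit | Logit-Wald limit | Claim |
|---|---|---|---|---|
| 25/30, all dispensed | 83.3% | 65.3% | 65.7% | no |
| 25/26, completers | 96.2% | 80.4% | 77.2% | yes |
| 40/50, all dispensed | 80.0% | 66.3% | 66.7% | no |
| 40/45, completers | 88.9% | 75.95% | 75.95% | yes |

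**4. False-claim rate at a true 75%.** This is P(lower limit > 0.75). For all dispensed, X ~ Bin(n, 0.75). For completers, M ~ Bin(n, 1 − d) and X given M ~ Bin(M, 0.75/(1 − d)).

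| Class size and method | All dispensed | Completers, 5% dropout | 10% | 15% |
|---|---|---|---|---|
| 30, exact | 1.06% | 4.10% | 10.77% | 24.92% |
| 30, logit-Wald, all-success sample not estimable | 1.04% | 3.44% | 7.41% | 14.33% |
| 30, logit-Wald, all-success sample counted as a pass | 1.06% | 3.56% | 8.17% | 18.57% |
| 25, exact | 0.70% | 2.73% | 8.89% | 23.14% |
| 25, logit-Wald, not estimable | 0.63% | 1.30% | 1.58% | 1.45% |
| 25, logit-Wald, counted as a pass | 0.70% | 1.68% | 3.30% | 8.63% |
| 15 or 20, logit-Wald, not estimable | 0 | 0 | 0 | 0 |

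**5. Deviation exclusions.** These can offset the effect. With 20 dispensed, 15 successes and 1 non-completer, completers give 15/19 = 78.9%; removing four successful completers as well gives 11/15 = 73.3%. In the 30-subject example it would take 20 such removals to return to 83.3%: (25 − 20)/(26 − 20) = 5/6.

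**The case against.** The strongest case concerns consequence. The study is exploratory, unpowered and single-site, with an approved lens, and its data are meant for designing later studies. Section 14.5 specifies a logit model, not an exact interval. Under the logit-Wald version with all-success samples not estimable, the false-claim rate is zero for classes of 15 or 20 and below 2.5% at 25; it exceeds that only in larger classes, such as 30 of 50. The two worked examples were chosen to show a reversal, and the second clears 75% by only 0.95 points. This stands: the size of any inflation is conditional and cannot be known from the plan. It does not remove the contradiction, and the plan still states a 75% hypothesis and a superiority rule.

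Second, the quantity tested is a least-squares mean that may be adjusted for age, sex or add power. The inequality in step 1 is exact for the crude proportion only; for the adjusted one an upward shift is expected but not guaranteed. This also stands.

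Third, section 14.9 implies some set wider than completers, because a completers-only set holds no dropouts to impute. But it names neither the variable nor the population, does nothing at or below 15%, and does not replace the primary test. Section 2.2 also already fixes the outcome of a non-completer, so nothing there needs imputing.

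Fourth, some non-completers stop for reasons unrelated to the lens, such as pregnancy or loss to follow-up. They are unsuccessful only by definition, which calls for a sensitivity analysis rather than for dropping all non-completers.

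**Conclusion.** The concern holds. The primary endpoint definition and the primary analysis population contradict each other, and the choice between them can decide the primary conclusion. Taken alone, the completion requirement can only raise the crude success proportion: by 3.9, 8.3 or 13.2 percentage points at 5%, 10% or 15% dropout if the true value is 75%. Whether the false-claim rate passes 2.5% depends on the assumed class size and interval method; with 30 in the class it does at each dropout rate examined, under both methods. The contradiction itself rests on none of these assumptions. It needs correcting before the analysis is run.

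**What to change.** In sections 14.2 and 14.3, assign the primary and secondary analyses to all subjects dispensed study lenses, score non-completers as unsuccessful in line with 2.2, and keep per-protocol as a sensitivity analysis.

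State why dispensing is the denominator: the objectives in 2.1 concern classification after lens wear, and the synopsis and 4.3 set the target in subjects dispensed. This is a choice, since subjects who fail fitting at Visit 2 also fail the definition in 2.2 and fall within the safety set ("All Subjects who were administered any test article excluding Subjects who drop out prior to administering any test article"). Report their number and reasons separately, and add a sensitivity analysis counting them as unsuccessful. For example, two such subjects turn 25/30 into 25/32 = 78.1%, exact lower limit 60.0%.

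In 14.9, name the variables to be imputed and the population, and state that the success classification of non-completers is not imputed. Add a sensitivity analysis that sets aside lens-unrelated discontinuations, using the reason recorded at step F.4.

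The same amendment can reconcile two related points: 5.2 and 8.2 disagree on replacing discontinued subjects, and the 50 in 14.2 are completers whereas those in 4.3 are subjects dispensed.

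The cost is an amendment to the protocol, submitted to the ethics committee under 18.3 where appropriate. No new data are needed: Quest is collected at Visit 1 (step 1.10), and discontinuation reasons and MRD at the Final Evaluation. Lens-on measurements may be missing for early dropouts, so the number analysed must be given for each predictor. The reported success rate will probably be less favourable.

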8. SUBJECTS COMPLETION/WITHDRAWAL

8.1. Completion Criteria

Subjects are considered to have completed the study if they:

- provided informed consent
- they are eligible
- they have completed all 6 study visits (V1-V6) through the final visit
- have not withdrawn/discontinued from the study for any reason described in Section 8.2

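### The Safety Population is assigned to no output, and section 14.2 read as written puts the safety summaries on completers only

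*Combined protocol and SAP*

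**What the plan says.** - **Population rule.** Section 14.2 (Sample Size Justification) ends with "All analysis will be conducted on the per-protocol population defined in section 14.3".
- **Per-protocol set.** Section 14.3 defines it as "All Subjects who have successfully completed all visits and did not substantially deviate from the protocol".
- **Safety Population.** Section 14.3 defines it as "All Subjects who were administered any test article excluding Subjects who drop out prior to administering any test article", with at least one observation on record. No section attaches an output to it. Sections 14.5 and 14.6 cover only the success models, 14.7 and 14.8 are marked not applicable, and there is no safety-analysis section.
- **Safety summaries.** Section 14.1 says: "Summary tables (descriptive statistics and/or frequency tables) will be provided for all baseline variables, efficacy variables and safety variables as appropriate". It names no population. It has unscheduled visits summarised separately, again with no population named.
- **Withdrawal.** The reasons listed in 8.2 include "Subjects presenting with a Corneal Infiltrative Event (CIE), or an eye infection", "Participant develops significant or serious adverse event during the study visit" and "Subject develops significant or serious adverse events causing discontinuation of study lens wear".
- **Completion.** Section 8.1 counts as completers only subjects who, among other conditions, "have not withdrawn/discontinued from the study for any reason described in Section 8.2".

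**The concern.** Safety is normally summarised on everyone exposed, because the subjects who stop are often the ones who had the event. Here the only sentence in section 14 that assigns a population to any analysis names a completers' set, and 8.2 makes certain ocular events a reason for not completing. A programmer who applies 14.2 literally would produce safety tables from which those subjects are missing because of the population rule. A low or zero rate in such a table would say little about the lens. This is separate from how the population choice affects the success endpoint.

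**Working it through.** **Plan's own figure.** There is none to reproduce. Section 14.2 gives 75 to enrol and 50 to complete, and says that no power analysis was used. No section gives an expected adverse-event rate.

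**Step 1: who is in which set.** The definitions in 8.1, 8.2 and 14.3, applied to each type of subject:

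| Subject | Safety Population | Per-protocol |
|---|---|---|
| Completes all visits, no substantial deviation, with or without an adverse event | In | In |
| Lenses inserted at Visit 2 (step 2.11), then stopped on fit or dispensing criteria (steps 2.17, 2.23) | In, if an observation is recorded | Out |
| Infiltrative event or eye infection, withdrawn under 8.2 | In | Out |
| Significant or serious event at a visit, or stopping lens wear, withdrawn under 8.2 | In | Out |
| Significant or serious event meeting neither 8.2 condition, or subject kept on under 13.3 | In | Possibly in |
| Pregnancy after lens wear (recorded as an adverse event, then discontinued, 13.5) | In | Out |

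The two sets therefore differ systematically in the subjects whose events ended participation.

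**Step 2: does the 14.2 sentence reach the safety tables?** Section 14.1 speaks of the analysis of data as including summarisation, which supports reading 14.2 as covering them. Elsewhere 14.1 lists summaries and statistical analyses as two things, which supports reading 14.2 as covering only the models. No text settles it. Under the first reading the safety tables are on completers. Under the second they have no stated population.

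**Step 3: size, with assumed counts.** Inputs: 50 subjects dispensed (section 4.3) and k subjects withdrawn under 8.2 for such an event (assumed). All other subjects are taken to be in the per-protocol set. The Safety Population shows k/50, and the per-protocol set shows 0/(50 − k). Limits are exact (Clopper-Pearson, two-sided 95%).

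| k (assumed) | Safety Population | 95% limits | Per-protocol | Upper limit |
|---|---|---|---|---|
| 1 | 1/50 = 2.0% | 0.1% to 10.6% | 0/49 | 7.3% |
| 3 | 3/50 = 6.0% | 1.3% to 16.5% | 0/47 | 7.5% |
| 5 | 5/50 = 10.0% | 3.3% to 21.8% | 0/45 | 7.9% |

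Subjects fitted but not dispensed are also exposed, so the Safety denominator can exceed 50. The documents do not say how many there will be. If all of the approximately 75 screened were fitted (an upper bound), 3 events would be 3/75 = 4.0%. The range for k = 3 is then 4.0% to 6.0%.

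**Step 4: how likely is at least one such event?** With an assumed true rate p among 50 subjects, the probability is 1 − (1 − p)^50. This gives 0.395 at 1%, 0.636 at 2%, 0.923 at 5% and 0.995 at 10%. When every such subject is withdrawn, the per-protocol count is 0 at each of these rates.

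**The case against.** **The sentence may not concern safety.** It sits in the sample-size section, and no section says outright that safety tables use the per-protocol set. Section 14.4 uses almost the same phrase for work controlled at a 5% type I error rate, which points to the success models. This is a fair reading, and it rules out saying that the plan explicitly places safety on completers. It does not supply the missing assignment. If the literal reading governs, moving the tables would be a change that 14.10 requires to be documented and justified.

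**A reader might infer that the safety report is emptied of the events that matter, or that infiltrative events and infections are certain to show as zero.** The documents do not support that:
- Withdrawal for significant or serious events is conditional in 8.2. Section 13.3 leaves continuation after an adverse event to the investigator's judgment.
- Section 13.1 classes non-significant infiltrative events and conjunctivitis among events that usually do not lead to stopping the lens, which sits uneasily with 8.2.
- An event first seen at the Visit 6 slit-lamp step, the last of that visit, might be found in a subject who still counts as a completer.
- Adverse events in completers stay in the tables, and the separate summary of unscheduled visits is not tied to the per-protocol set.
- Sections 13.3 and 13.4 require every event to be documented and reported to the sponsor.

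**A reader might also infer that the plan treats these events as its main ocular risks.** It does not say so. Section 1.4 calls the study minimal risk with a marketed lens, 13.4.3 expects no events of special interest, and safety is not among the objectives or endpoints in section 2.

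Section 14.1 names no adverse-event or slit-lamp table, only safety variables in general. What stands is the gap in the assignment and the direction of the error if 14.2 is applied literally.

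**Conclusion.** The point holds as a defect in population assignment. The Safety Population is defined and left unused, and the one population rule in section 14, read as written, removes exposed non-completers from the safety summaries. What is lost is their contribution to the reported rates; the trial record keeps the events. The size cannot be estimated from the documents. The 6.0% against 0/47 comparison rests on an assumed 3 events, on 50 exposed subjects, and on 8.2 being followed for each of them. The plan should be amended, because the error runs in one direction and is cheap to remove. The success analyses do not depend on this correction.

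**What to change.** 1. In 14.2, limit the per-protocol sentence to the success analyses in 14.5 and 14.6, by name.
2. In 14.1 or 14.3, state that adverse events, slit-lamp findings, acuity loss and discontinuations due to adverse events are summarised on the Safety Population. Include findings from unscheduled visits and the Final Evaluation, and use the number exposed as denominator.
3. Reconcile the withdrawal list in 8.2 with the investigator-judgment text in 13.3, so that it is clear which subjects leave after an event. Which rule should apply is a clinical matter for the sponsor and the investigator.

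The statistical changes cost one or two sentences in section 14 and a different population flag in the safety tables; the data are already collected. The downside is that the reported event rate may look less favourable.
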